### **5.5.1 Permitted Concomitant Therapies**

The Investigator may prescribe concomitant medications or treatments deemed necessary to the subject without any impact on study participation, with the exception of those medications defined in Section 5.5.2 of this protocol.

Subjects who start any non-buprenorphine MAT or transmucosal buprenorphine treatment will not be discontinued from the study. Information on MAT initiation, dosing regimen, potential changes in dose and cessation of therapy must be documented.

### **5.5.2 Prohibited Concomitant Therapies**

If subjects initiate treatment with SUBLOCADE or any other long-acting buprenorphine product during the study, they will be discontinued from the study and no further samples will be collected.

## 6 STUDY CONDUCT

Study assessments and procedures, including the timing of assessments, are summarised in Appendix 1 – Schedule of Events.

### 6.1 Subject Enrolment

Study participation begins once written informed consent is obtained. Subject identification numbers will be carried over from the previous Phase III SUBLOCADE study in which the subject participated. The subject identification numbers will be used to identify the subject during the screening process and throughout study participation.

The Investigator is responsible for maintaining a master list (i.e., a subject identification list) of all consented subjects and will document all subjects who did not meet study eligibility criteria (i.e., screen failures), including reason(s) for ineligibility (i.e., a subject screening and enrolment log). This document will be reviewed by Indivior or designated representative for accuracy and completeness. Ineligible subjects, as defined by the protocol-specific inclusion and exclusion criteria, should be documented as screen failures.

### 6.2 Screen Failure

A subject will be considered a screen failure if written informed consent is obtained but the subject does not meet eligibility criteria for Part A.

### 6.3 Subject Completion

A completed subject for Part A is one who has completed all of the plasma and urine assessments for Part A (i.e., Visit 1).

A completed subject for Part B is one who has completed all of the plasma and urine assessments at both visits for Part B.

### 6.4 Withdrawal and Stopping Criteria

Part A consists of a single visit (Visit 1) so there are no withdrawal or stopping criteria except subject withdrawal of consent (see Section 6.4.2).

#### 6.4.1 Subject Withdrawal from the Study

For subjects who participate in Part B, the subject will continue the study until he or she meets one of the following criteria:

- The subject completes both visits in Part B.
- The subject discontinues study participation for any reason or misses the 2 visits, or the Sponsor decides to terminate the subject's participation or modifies the duration of the study.

Part B may meet enrolment and be considered closed to new subjects while Part A is still open to enrolment.

If the subject has permanently discontinued his or her participation in the study and is no longer being followed for study assessments and procedures (including follow-up procedures), he or she will be considered withdrawn from the study. The primary reason for withdrawing from the study must be entered into the eCRF (e.g., subject is lost to follow-up, Indivior terminates the study).

#### **6.4.2 Subject Withdrawal of Consent**

If a subject withdraws consent, he or she will no longer be followed for study assessments and will be considered withdrawn from the study. The primary reason for withdrawing from the study must be entered in the eCRF.

#### **6.4.3 Subjects Lost to Follow-up**

In cases of a missed visit, the Investigator or designee must attempt to contact the subject and re-schedule as soon as possible. The Investigator or designee must counsel the subject on the importance of maintaining the assigned visit schedule and ascertain whether or not the subject wishes to and/or should continue in the study.

In the event that a subject is lost to follow-up, the Investigator or designee must make a reasonable effort to contact the subject. Two documented attempts (e.g., phone, email, etc.) to contact the subject followed by a certified mailed letter is considered reasonable.

For the purpose of documenting the date of discontinuation for a subject confirmed to be lost to follow-up, the date of discontinuation should be the date of last contact with the subject.

- In the case where a certified letter is sent but not confirmed as received by the subject, the date of discontinuation is the date the certified letter was sent.
- In the case where a certified letter is sent and has been confirmed as received by the subject, the date of discontinuation is the date of the confirmed subject receipt.
- In the event that neither of these above cases applies (which should be explained in the source documents), the date of discontinuation is the date of the subject's last study visit.

## **7 STUDY SUSPENSION OR TERMINATION**

Indivior reserves the right to temporarily suspend and/or permanently discontinue the study at any time and for any reason, including safety or ethical concerns or severe noncompliance. If such action is taken, Indivior will discuss the rationale for the decision with the Investigator. In cases where a study is suspended or terminated for safety reasons, Indivior will promptly inform Investigators and the Regulatory Authorities of this action and the reason(s) for the suspension or termination.

If required by applicable regulations, the Investigator must inform the Institutional Review Board (IRB) promptly and provide the reason(s) for the suspension or termination.

## **8 DESCRIPTION OF STUDY PROCEDURES**

Study assessments and procedures, including the timing of assessments, are summarised in Appendix 1 – Schedule of Events. Further details on PK, clinical and safety assessments are provided in Sections 8.2, 8.3 and 8.4, respectively.

A signed written informed consent form must be obtained from the subject before any study assessments or procedures may be performed. At Screening, if an assessment or procedure has already been performed as part of routine standard of care and was completed within the protocol-specific screening window, the assessment or procedure does not need to be repeated, unless clinically indicated. All assessments and procedures may be performed more frequently, if clinically indicated.

### **8.1 Demographics and Medical History**

A detailed medical and psychiatric history since the end of the previous participation in Phase III SUBLOCADE study will be obtained during the Screening period. This will include information regarding the subject's history of relevant medical conditions, diagnoses, procedures, treatments and any other noteworthy medical information. Height and body weight will also be collected, and body mass index will be calculated in the eCRF. Any updates to medical history information made available during the course of the study will be captured. Demographics, medical and psychiatric history will be recorded in the source documents and the eCRF per Appendix 1 – Schedule of Events.

### **8.2 Pharmacokinetic and Clinical Assessments**

#### Part A

Visit 1 (same day as Screening) PK and clinical assessments will be as follows:

- collection of a blood sample for the determination of buprenorphine and norbuprenorphine plasma concentrations.
- collection of a urine sample for determination of free buprenorphine and free norbuprenorphine concentrations; qualitative UDS for opioids, including buprenorphine; quantitative UDS for buprenorphine, norbuprenorphine and naloxone; and determination of creatinine concentration.

#### Part B

At each visit, the same assessments as in Part A will be performed:

- collection of a blood sample for the determination of buprenorphine and norbuprenorphine plasma concentrations.

- collection of a urine sample for determination of free buprenorphine and free norbuprenorphine concentrations; qualitative UDS for opioids, including buprenorphine; quantitative UDS for buprenorphine, norbuprenorphine and naloxone; and determination of creatinine concentration.

In addition, the subject will answer a question regarding his or her illicit use of buprenorphine within the last 14 days.

### **8.2.1 Sample Collection, Storage, and Shipping**

Details for the collection, preparation, storage and shipment of laboratory specimens will be outlined in the laboratory manual.

### **8.2.2 Plasma Samples for Pharmacokinetic Analysis**

Blood samples for PK analysis of buprenorphine and norbuprenorphine will be collected at the time points listed in Appendix 1 – Schedule of Events. The actual date and time of each sample collection will be documented. For each PK sample, 6 mL of blood will be collected into K2-EDTA tubes. After centrifugation of the tubes, the resulting plasma will be separated into aliquots (primary and back-up). The primary aliquot will be sent to the bioanalytical laboratory for the determination of buprenorphine and norbuprenorphine plasma concentrations. Details about sample processing, storage and shipping procedures are provided in the laboratory manual.

### **8.2.3 Urine Samples for Pharmacokinetic Analysis and Qualitative UDS**

Urine samples will be collected at the time points listed in Appendix 1 – Schedule of Events. Efforts will be made to collect urine samples under similar conditions across visits.

The following aliquots will be prepared from each urine sample:

- Aliquots (primary and back-up) will be sent to the bioanalytical laboratory for the determination of free buprenorphine and free norbuprenorphine concentrations in urine.
- Additional aliquots will be prepared and sent to the diagnostic laboratory who will perform 3 analyses: 1) qualitative UDS for opioids, including buprenorphine; 2) quantitative UDS for buprenorphine, norbuprenorphine and naloxone; and 3) determination of creatinine concentration in urine.

All details related to urine collection (including volume of urine collected), sample processing (preparation of aliquots), storage and shipping procedures are provided in the laboratory manual.

### **8.2.4 Sample Analysis**

The analysis of plasma samples will be performed by a bioanalytical laboratory using a validated liquid chromatography with tandem mass spectrometry method for the determination of buprenorphine and norbuprenorphine concentrations in plasma.

The analysis of urine samples will be conducted by 2 laboratories:

- a bioanalytical laboratory for the determination of free buprenorphine and free norbuprenorphine concentrations in urine, using a validated liquid chromatography with tandem mass spectrometry method;
- a diagnostic laboratory for 1) qualitative UDS for opioids, including buprenorphine; 2) quantitative UDS for buprenorphine, norbuprenorphine and naloxone; and 3) determination of creatinine concentration in urine.

Raw data generated by the bioanalytical laboratory will be archived at the bioanalytical site. The results of analyses performed by the diagnostic laboratory will be archived as described in the laboratory manual. Additional methodologies will be summarised in the clinical study report (CSR).

### **8.3 Clinical Assessments**

Clinical assessments will include UDS for opioids (described in Section 8.2) and self-reported use of illicit buprenorphine within the last 14 days.

### **8.4 Safety Assessments**

All adverse events (AE) associated with study assessments and/or study conduct will be collected using the Adverse Event eCRF. All serious AEs (SAEs) associated with the study assessments and/or study conduct will be collected using the Safety Information Collection Form.

Concomitant medications will be collected, including any prescribed MAT (inclusive of any MATs that lead to study discontinuation, such as long-acting buprenorphine treatment).

Illicit use of buprenorphine will be captured separately outside of the Concomitant Medication eCRF.

See Section 12 for details of pregnancy assessments.

### **8.5 Appropriateness of Measurements**

All of the safety assessments in this protocol are standard. The PK assessments have been used for quantification of buprenorphine and norbuprenorphine concentrations in plasma in previous registration studies for SUBLOCADE. The PK assessments are being used to assess the long-term plasma exposure to buprenorphine after stopping SUBLOCADE treatment and to refine the existing population PK model of SUBLOCADE. Some of the UDS assessments were also used in these prior registration studies. Together with plasma concentration data, urine results will be used to evaluate the relationships between drug plasma concentrations, free drug concentrations in urine, and UDS results for buprenorphine from a diagnostic laboratory.

## 8.6 Protocol Deviations

A protocol deviation is any noncompliance with the clinical study protocol or ICH/GCP requirements. The noncompliance may be on the part of the subject, the Investigator, or the study site staff. As a result of deviations, corrective actions are to be developed by the site and implemented promptly and in accordance with ICH E6. It is the responsibility of the Investigator and study site staff to use continuous vigilance to identify and report deviations to Indivior or specified designee and the IRB. All deviations must be addressed in the study source documents. Protocol deviations must be sent to the central IRB in accordance with the central IRB's requirements. The Investigator and study site staff are responsible for knowing and adhering to the IRB's requirements.

## 9 STUDY DRUG MANAGEMENT

This is an observational study with no drug intervention.

## 10 ADVERSE EVENTS

The Investigator or designee is responsible for identifying, documenting and reporting events that meet the definition of an AE.

deat

In addition, any AE or SAE of which the Investigator becomes aware that pertains to SUBLOCADE or SUBOXONE use, or related to participation in a previous SUBLOCADE clinical study, will be reported via completion of the Safety Information Collection Form and that form will be sent to the following email address: [[contact]](mailto:[contact]).

Events meeting the definition of an AE associated with study assessments and/or study conduct include the following:

- new condition detected after study assessment and/or associated with study conduct even though the AE may have been present prior to the study assessment or study participation;
- exacerbation of a pre-existing condition (including intensification of a condition and/or an increase in frequency) resulting from a study assessment and/or study conduct;
- any safety assessments resulting from a study assessment and/or study conduct felt to be clinically significant in the opinion of the Investigator (including those that worsen from baseline);
- symptoms and/or clinical sequelae resulting from a study assessment and/or study conduct that resulted in intervention.

Events that do not meet the definition of an AE include:

- the disease/disorder being studied, or expected progression, signs, or symptoms of the disease being studied, unless more severe than expected for the subject's condition;
- medical or surgical procedures; the condition that leads to the procedure is an AE;
- situations where an untoward medical occurrence did not occur (e.g., social and/or convenience admission to a hospital, hospitalization for elective surgery, hospitalization for observation in the absence of an AE);
- anticipated day-to-day fluctuations of pre-existing disease(s) or condition(s) present or detected at the start of the study that do not worsen.

## **10.1 Assessment of Adverse Events**

The Investigator is ultimately responsible for assessing and reporting all AEs as outlined in the protocol. The assessment and reporting of AEs may be delegated to a medically qualified sub-Investigator, trained on this study protocol, who is listed on the delegation of authority log.

Adverse events should be volunteered by the subject or obtained from observation of the subject at a site visit. If an event requires intervention, or if in the opinion of the Investigator it is clinically significant, then it will be reported as an AE (using the Adverse Event eCRF).

All AEs are to be assessed and recorded in a timely manner and followed to resolution or until the Investigator determines that there is not an anticipated resolution. Each AE is to be documented with reference to severity, date of occurrence, duration, treatment and outcome. Furthermore, each AE is to be classified as being serious or non-serious.

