## 1.4 Risk-Benefit Assessment

This is an observational study with no drug intervention. The risks in this study are minimal, given that assessments are based on a single blood sample and a single urine sample for subjects in Part A. Subjects progressing to Part B will provide a maximum of 2 additional blood samples and 2 additional urine samples taken at 2 subsequent monthly visits. The risks involved in collecting venous blood samples may include possible bruising, redness and swelling around the site of blood withdraw; bleeding at the site; feeling of light-headedness when the blood is drawn; and rarely, an infection at the site. Results of urine assessments relative to buprenorphine and other opioids will remain confidential.

The study does not provide direct benefit to the study subjects; however the results of the study will inform patients and physicians on how long buprenorphine remains at quantifiable concentrations in plasma after the last dose of SUBLOCADE, as well as clarifying the relationship with positive UDS for buprenorphine.

Based on ongoing review of the data, the Sponsor reserves the right to modify the duration of the study at any time.

The study will be carried out in accordance to the protocol and with local legal and regulatory requirements, International Council for Harmonisation E6 / Good Clinical Practice (ICH/GCP) guidelines and all applicable subject privacy requirements.

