### **10.1.1 Time Period for Collecting Adverse Events**

Adverse events will be collected from the time of signed informed consent until completion of the subject's last visit.

Subjects with SAEs related to study procedures ongoing at the end of the study or after early termination will be followed by the Investigator until stabilization or resolution. If a subject experiences the onset of an SAE assessed by the Investigator as related to study procedures within a period of 30 days following study completion or withdrawal, the Investigator will follow the procedures defined in Section 10 and Section 11 for assessing, documenting, and reporting these events.

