## 22 APPENDICES

### Appendix 1 – Schedule of Events

	Screening	Part A	END OF PART A Subjects can proceed into Part B only if they meet continuation criteria b	Part B	
Visit		Visit 1 a		Visit 2	Visit 3 a
Day	Day 1 c	Day 1 c		30 days from Visit 1 ±7 days	30 days from Visit 2 ±7 days
Visit Window					
Informed Consent	X				
Demographics	X				
Eligibility Criteria	X				
Body Weight		X			
Height		X			
Body Mass Index (calculated in eCRF)		X			
Medical History d		X			
Urine Sample e		X		X	X
Urine Pregnancy Test f		X		X	X
Blood (PK) Sample		X		X	X
Adverse Events g		X		X	X
Concomitant Medications h		X		X	X
Buprenorphine Question i				X	X

eCRF=electronic case report form; PK=pharmacokinetic

a Visit 1 acts as the End of Study visit for Part A and Visit 3 acts as the End of Study visit for Part B. If a subject experiences the onset of a serious adverse event assessed by the Investigator as related to study procedures within a period of 30 days following study completion or withdrawal, and the Investigator will follow the procedures defined in Section 10 and Section 11 for assessing, documenting, and reporting these events.

b Subjects who achieve negative results for both buprenorphine and norbuprenorphine quantitative UDS (irrespective of naloxone result) at Visit 1 will conclude their study participation, as will subjects who achieve a positive result for buprenorphine and/or norbuprenorphine and a positive result for naloxone on the quantitative UDS performed at Visit 1. Subjects who achieve a positive result for buprenorphine and/or norbuprenorphine and a negative result for naloxone on the quantitative UDS performed at Visit 1 can continue into Part B of the study if Part B is still open to enrolment.

c The Screening visit becomes Visit 1 for subjects eligible to enter Part A (that is, those that are not screen failures).

d Medical history since end of previous participation in Phase III SUBLOCADE study.

e From the urine sample collected, aliquots will be sent to the bioanalytical laboratory; additional aliquots will be prepared and sent to the diagnostic laboratory; if applicable, the remaining urine will be used for a dipstick pregnancy test.

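### No question about events since the last visit is specified at Visits 2 and 3, so AEs that clear between visits depend mainly on unprompted report

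*Protocol*

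**What the plan says.** Protocol 8.4 sets a broad target: "All adverse events (AE) associated with study assessments and/or study conduct will be collected using the Adverse Event eCRF". Protocol 10.1.1 makes the period continuous: "Adverse events will be collected from the time of signed informed consent until completion of the subject's last visit". The days between visits are therefore in scope.

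The method is in Protocol 10.1: "Adverse events should be volunteered by the subject or obtained from observation of the subject at a site visit". The next sentence sets a reporting threshold: "If an event requires intervention, or if in the opinion of the Investigator it is clinically significant, then it will be reported as an AE".

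Protocol 1.4 lists the expected harms of venous sampling. They include "possible bruising, redness and swelling around the site of blood withdraw", bleeding at the site, light-headedness during the draw and, rarely, infection.

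Appendix 1 of the protocol schedules AEs at Visits 1, 2 and 3. Visit 2 falls "30 days from Visit 1 ±7 days" and Visit 3 falls "30 days from Visit 2 ±7 days". The only scripted subject question at Visits 2 and 3 is about illicit buprenorphine use. SAP 12.1 reports AEs as numbers and percentages of subjects for the Part A and Part B cohorts, and states no limitation on how the events were found.

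**The concern.** The aim in 8.4 is wider than the method in 10.1 can be relied on to deliver. Several of the harms named in 1.4 can come and go within days. When the subject returns about a month later there may be nothing to observe, which leaves the subject's unprompted recall as the main route.

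Sampling is the study's only intervention, so procedure-related AEs are the main safety information it can yield. If some are missed, the percentages in the SAP tables are too low, and nothing in the SAP tells the reader so. In a multicentre study, leaving the question to local habit may also make ascertainment uneven between sites. Finally, staff may not learn of a problem at the previous draw site before they draw again.

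**Working it through.** The plan gives no AE rate, precision target or volunteering rate, so there is no figure of its own to reproduce. The check has four steps.

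**1. Interval between a draw and the next visit** (Appendix 1: 30 days, ±7).
30 − 7 = 23 days; 30 + 7 = 37 days.

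**2. Number of draws affected** (Protocol 5.1: about 60 subjects in Part A, at most 30 in Part B; one draw per visit). These are maxima and assume that Part B fills and all visits are completed.
- All draws: 60 (Visit 1) + 30 (Visit 2) + 30 (Visit 3) = 120.
- Followed by a later visit: 30 (Visit 1 draws of subjects who go on) + 30 (Visit 2 draws) = 60 intervals.
- Not followed by a later visit: (60 − 30) + 30 = 60, or 60/120 = 50%. These raise a separate matter, when collection ends, and are not part of this point.

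**3. Which 10.1 route can reach an event that has cleared by day 23 to 37?**
- Observation at the visit: not for a resolved bruise, redness, swelling, bleed or infection.
- Volunteering: yes, if the subject thinks to mention it.
- Elicitation: not specified in the protocol or the SAP.
- Indirect: a treated event may surface through the concomitant medication record (Protocol 5.5) or a medical history update (Protocol 8.1).

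Light-headedness does not belong in this group. Protocol 1.4 ties it to the moment of the draw, when staff are present and can observe it.

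**4. Can the loss be sized?** Let p be the per-draw risk of a reportable event that resolves before the next visit, and s the share of such events that is volunteered. Both are assumptions. The two draws are treated as independent with equal risk, and the indirect route is ignored. For 30 Part B subjects over two draws:

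- expected with an event = 30 × [1 − (1 − p)²]
- expected to be recorded = 30 × [1 − (1 − ps)²]
- missed = the difference

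Example with p = 5% and s = 50%: 30 × (1 − 0.95²) = 2.9; 30 × (1 − 0.975²) = 1.5; missed = 1.4 (from unrounded values).

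| p | Expected subjects | Missed, s = 100% | Missed, s = 50% | Missed, s = 0% |
|---|---|---|---|---|
| 1% | 0.6 | 0 | 0.3 | 0.6 |
| 5% | 2.9 | 0 | 1.4 | 2.9 |
| 10% | 5.7 | 0 | 2.8 | 5.7 |

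Over this grid the loss runs from none to 5.7 subjects. The documents contain nothing that fixes p or s, so no cell can be preferred. Only the direction is informative: relying on unprompted report can lose such events but cannot add any.

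**The case against.** A reader might infer that subjects are never asked about such events and that AE incidence is under-counted as a matter of fact. The documents support neither reading.

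- AEs are a scheduled item at every visit. Protocol 10 makes the Investigator or designee responsible for identifying them, and 10.1 does not forbid asking. Protocol 16 refers to CRF completion guidelines, which are not among the documents, so a prompt may exist there.
- An event that cleared between visits can still be volunteered at the next one, and one that was treated may show up in the medication record.
- The 10.1 threshold matters. A trivial bruise may not be reportable even if asked about, and an event that needed treatment is one a subject may be more likely to mention.
- The AE tables are not the only safety output. The plan also covers deaths and pregnancy tests (SAP 12.1.2 and 12.4.1) and concomitant medications (SAP 11).
- The study is observational and makes no formal tests (Protocol 14.1), and its primary endpoint is a concentration plot (Protocol 3).

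These arguments limit the point but do not remove it. The schedule says when AEs are recorded, not how they are found; 10.1 is the only text on method. The threshold is applied by the Investigator, who cannot apply it to an event nobody raised.

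**Conclusion.** The point holds as a minor, inexpensive improvement in method. Followed as written, 10.1 leaves events that clear before Visit 2 or Visit 3 to unprompted report, with some indirect help from medication and history records. At most 60 post-draw intervals are affected. The likely effect on AE incidence is downward and its size is unknown.

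This rests on two assumptions: that sites follow 10.1 as it stands, with no prompt supplied by study materials outside these documents, and that at least some reportable draw-site events resolve within 23 to 37 days. The consequence is modest. It touches the descriptive safety tables and leaves the pharmacokinetic results unaffected.

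**What to change.** Amend the ascertainment sentence in Protocol 10.1 so that AEs may be volunteered, observed, or elicited by one standard non-leading question. At Visits 2 and 3 staff ask it before the blood draw, about any problems since the last visit. They ask again after sample collection at every visit.

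State that elicited events are assessed under the existing 10.1 reporting criteria in the same way as volunteered or observed ones. This clause is needed: an edit that sent every elicited event straight to the AE eCRF would contradict the threshold in the sentence that follows.

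The cost is a short change to 10.1 and a line in the visit instructions. No visit, sample or procedure is added, and a scripted question is already put to subjects at Visits 2 and 3. The small downside is a few more mild or incidental reports to assess for relation to study procedures. If the protocol is not amended, the SAP and study report should at least say that AE incidence reflects spontaneous or observed events and is likely a lower bound.
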